### 3.3 Exclusion Criteria

- a) Prior surgical resection of any pancreatic malignancy
- b) Prior invasive malignancy (except non-melanomatous skin cancer) unless disease free for a minimum of 3 years
- c) Any prior chemotherapy or radiation for treatment of the patient's pancreatic tumor.
- d) Prior radiotherapy to the region of the study cancer that would result in overlap of radiation therapy fields
- e) Severe, active comorbidity, defined as follows:
  1. Unstable angina and/or congestive heart failure requiring hospitalization within the last 12 months
  2. Transmural myocardial infarction within the last 6 months
  3. Acute bacterial or fungal infection requiring intravenous antibiotics at the time of registration
  4. Chronic obstructive pulmonary disease exacerbation or other respiratory illness requiring hospitalization or precluding study therapy within 30 days prior to registration.
- f) Severe, uncorrectable hepatic insufficiency and/or coagulation defects due to liver failure
- g) Any evidence of distant metastases (M1)
- h) Pregnancy or women of childbearing potential and men who are sexually active and not

willing/able to use medically acceptable forms of contraception; this exclusion is necessary because the treatment involved in this study may be significantly teratogenic

#### **4. METHODS AND STUDY PROCEDURES**

##### **4.1 Pretreatment Evaluation (please see schedule in Appendix B for table layout)**

Within 6 weeks prior to study enrollment patients must undergo the following evaluations:

- a) History and physical by Radiation Oncologist, Gastroenterologist and Surgical Oncologist
- b) CT or MRI scan of the abdomen and pelvis with IV contrast or PET/CT
- c) CT chest or PET/CT within 6 weeks prior to registration
- d) Informed Consent obtained by a member of the study team
- e) Lab studies [CBC with diff, Na, K, BUN, Cr, Glucose, Phosphorous, Calcium, Albumin, AST, ALT, Total bilirubin, Alkaline phosphatase, CA19-9, CEA, INR and a pregnancy test (urine or serum HCG) for women of childbearing potential].
- f) If clinically indicated, fiducial placement in/near the tumor via endoscopic ultrasound by gastroenterology service at least one week prior to CT simulation
- g) Patients will be placed on proton pump inhibitors 1 week prior to SBRT to continue until the day of surgery to minimize bowel toxicity.
- h) Any bile stent manipulation should be done 7-10 days prior to SBRT

##### **4.2 Evaluation during study Period**

- a) History, physical and vital signs during the weekly “on treatment visit” during radiation therapy
- b) History, physical and vital signs and laboratory evaluation obtained by surgery team prior to resection. Specific tests needed will be determined by surgical team.
- c) Following resection, patients will be assessed within 30 days after discharge for post-operative morbidity by the surgery team.
- d) Patients will be followed at least every 6 months for a minimum of 5 years by a physician from either radiation, surgical or medical oncology service. Closer follow up may be needed based on clinical situation.

##### **4.3 Treatment**

###### **4.3.1 Radiation Therapy**

###### **4.3.1a Simulation and Planning**

Patients should abstain from oral intake for 2 hours prior to CT Simulation. Water and medications are acceptable. Patients will be simulated supine and Exac-trac body markers will be placed on the skin for patient positioning and respiratory management. In order to minimize treatment volume, patients will be asked to perform end-expiratory breath hold during simulation and treatment. If patient is unable to tolerate and/or comply with breath hold, simulation and treatment will be done using shallow free breathing. A Vac-bag custom immobilization device will be made.

With the patient in the treatment position and in end-expiratory breath hold, a non-contrast CT will be first performed. This will be followed by a contrast CT scan (if no contraindications) also using breath hold technique. The maximum slice thickness will be 2.5mm. If intravenous contrast is not used during CT Simulation, a diagnostic CT or MRI using intravenous contrast or PET/CT must be available as a reference for target delineation.

Gross tumor volume (GTV) will be defined on the basis of CT and MRI imaging findings. The GTV alone will be treated with a planning target volume (PTV) margin of -5 mm to account for setup inaccuracy and patient and organ movement. If needed, PTV can be reduced to 3mm or less in order to avoid high doses to the duodenum and stomach. 25 Gy in 5 fractions will be prescribed to the 70-90% isodose line. Patients will be treated in 5 fractions delivered over 5-7 days.

#### 4.3.1b Plan Evaluation

Prior to starting treatment, the radiation plan for each patient will be evaluated by the radiation oncologists who will review the isodose curves on the treatment planning scan and evaluate the dose-volume histograms (DVH).

#### Target Dose

25 Gy in 5 fractions will be prescribed to the 70-90% isodose line. The prescription isodose line will be chosen so that at least 95% of the PTV is conformally covered by the prescription isodose surface. Target doses less than 95% of prescription dose are limited to areas adjacent to an organ at risk (OAR).

[figure not shown]

Figure 1. Schematic of Radiation Prescription

1. Prescription dose 25 Gy
2. Prescription isodose 70-90%
3. At least 95% of PTV covered by prescription isodose
4. Normalization to be at isocenter

Normal Tissue Tolerance adapted from Chuong et al. :

- Mean kidney dose <10 Gy
- Duodenum/small bowel/stomach: maximum dose (0.5cc) <35 Gy, mean dose <20 Gy, volume receiving 30 Gy <5 cc
- Liver: volume receiving 30 Gy <10%
- Spinal cord maximum point dose -20 Gy

#### 4.3.1c Quality Assurance

The prescription isodose line selected will be 70-90% of the maximum dose within the PTV. As a result a “hotspot” will exist within the PTV that is equal to the prescription dose divided by the prescription isodose line (e.g.  $25 \text{ Gy}/0.8 = 31.25 \text{ Gy}$  when 25 Gy is prescribed to the 80% isodose line). Doses higher than the prescription dose (i.e. hotspots) must occur within the target and not within an OAR.

#### 4.3.1d Treatment

Patients will be immobilized in the Vac-Bag device. They will be treated in the manner in which they were simulated; either expiratory breath hold or shallow breathing. They will initially be positioned using ExacTrac body markers. Treatment position will then be confirmed by fiducials alignment via ExacTrac KV imaging. Final anatomic confirmation will be made by cone-beam CT immediately prior to treatment.

#### 4.3.2 Supportive Treatment During Radiation

- a) Narcotic pain medications and anti-nausea medications will be prescribed as needed
- b) NSAID medications will be stopped prior to SBRT and not restarted until after surgery.

#### 4.3.3 Surgery

Surgery will be performed no more than 3 weeks after completion of radiation therapy. A pancreaticoduodenectomy (Whipple procedure) with standard lymphadenectomy will be done. Restaging is not required prior to surgery. However if re-staging scans are obtained and demonstrate metastatic disease, surgery will not be performed.

An attempted resection may also be aborted when more advanced or metastatic disease is found at the time of laparotomy. If surgical resection cannot be completed due to the presence of advanced disease, the patient will be withdrawn from the protocol at that time and will continue their care with standard treatment and follow up based on their clinical characteristic.

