## **6.        ADVERSE EVENTS**

### **6.1      Definition of Adverse Event**

An adverse event is any symptom, sign, illness, or experience which develops or worsens during the course of the study, whether or not the event is considered related to the study intervention.

The investigator will be responsible for assessing the etiology of any adverse events and determining if these can be considered a treatment related adverse event (TRAE) which arose directly or indirectly as a result of SBRT. Adverse events will be graded according to the NCI CTCAE Version 4.0. TRAE will be considered “acute” if they occur within 1-4 weeks post SBRT and prior to surgical resection and “late” if they occur after this time period.

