## 6.3 Documentation of Adverse Events

All adverse events, whether observed by the Investigator, elicited from or volunteered by the subject, will be documented. Each adverse event will include a brief description of the experience, the date of onset, the date of resolution, the duration and type of experience, the severity, and the relationship to SBRT, contributing factors, and any action taken with respect to the planned radiation therapy. In addition, any toxicity leading to radiation treatment break and delay in surgical resection beyond 3 weeks post SBRT will be noted.

All patients are expected to undergo surgical resection within 3 weeks after radiation therapy. Any Intraoperative complications including blood loss, total operative time and amount of fibrosis noted by the surgeon will be recorded in the operative report. Post-operative complications including delayed wound healing, blood loss, infection, length of hospital stay, incidence of pancreatic leak, hospital readmissions for complications will also be recorded. Appendix A lists the data the surgical oncology team is responsible for recording.

Treatment related late complications including but not limited to duodenal and intestinal ulceration, perforation, gastritis, bowel adhesions and obstruction, will be recorded at follow ups up to 5 years after treatment.

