## 6.4 Serious Adverse Events (SAEs)

A serious adverse event is any adverse event that results in any of the following outcomes:

- death;
- is life-threatening;
- requires inpatient hospitalization or prolongation of existing hospitalization;
- results in persistent or significant disability/incapacity;
- is a congenital anomaly/birth defect; or
- requires medical or surgical intervention to prevent permanent impairment or damage.

Any serious adverse events will be communicated directly to the primary investigator ([name]) within 24 hours and documented in the patient's medical chart. [name] will determine how to respond to the event and whether the patient will continue on the study.

All SAEs will be reported to the IRB per local institutional policy.

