## **9. DATA ANALYSIS AND MONITORING**

The purpose of this pilot study is to determine feasibility of preoperative SBRT followed by surgical resection at URMC and to determine its safety and tolerability in a small population of patients. For this phase 1 trial, we plan to enroll 18 patients over 1-2 years with a goal of 12 evaluable cases. This is a generally accepted number of patients for phase 1 trials and will minimize the risks to patients in case the treatment is found to be unsafe. We will stop recruitment and analyze the safety data if there appears to be any grade 3 or greater toxicity on any subject that can be directly attributed to SBRT or if any patients are made ineligible for surgical resection solely due to toxicities from SBRT.

In the case where any patient becomes ineligible for resection due solely to toxicity from SBRT, the study will be immediately closed to accrual. We will stop recruitment and any patient who has not started radiation therapy will have their planned radiation treatment canceled. A patient who has started radiation therapy will undergo an individual discussion with [name] about the risks and benefits of continued treatment.

If a patient experiences grade 3 or greater toxicity directly attributable to SBRT that is reversible and ultimately able to undergo resection, we will analyze the event and attempt to prevent/reduce the adverse event from taking place again. We will discuss the risks and benefits of continued recruitment into the study with our co-investigators and determine whether or not to continue the study. If we believe that modifications can be made that will reasonably reduce the risk of a future event from occurring, we will continue recruitment to the study.

The investigators plan to evaluate the rates of acute toxicity after 12 patients have been enrolled and undergone SBRT and surgical resection. Long term safety and efficacy will be evaluated after all 12 patients have undergone surgical resection and have either been followed for at least 6 month or have died. The primary investigator, [name] will have access to all of the study data.

The Cancer Center Data & Safety Monitoring Committee will monitor the study for safety. Study

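### Irradiated patients withdrawn under 4.3.3 for advanced disease have no stated adverse event follow-up afterwards, so their SBRT-attributed grade 3+ events are not assured of reaching the Section 9 pause or the published late toxicity

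*Combined protocol and SAP*

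**What the plan says.** Section 4.3.3 plans surgery within 3 weeks of SBRT: "A pancreaticoduodenectomy (Whipple procedure) with standard lymphadenectomy will be done". If advanced disease prevents this, "the patient will be withdrawn from the protocol at that time and will continue their care with standard treatment and follow up". Restaging before surgery is optional, so advanced disease may first be found at laparotomy, after the full study intervention has been given.

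The follow-up rules are written for patients in general. Section 4.2(d) says "Patients will be followed at least every 6 months for a minimum of 5 years". Section 6.2 assesses adverse events at those visits. Section 6.3 says "Treatment related late complications including but not limited to duodenal and intestinal ulceration, perforation, gastritis, bowel adhesions and obstruction, will be recorded", for up to 5 years after treatment. None of the three mentions a patient who has left the protocol.

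Section 6.1 defines an adverse event as "any symptom, sign, illness, or experience which develops or worsens during the course of the study". Section 6.4 builds on that: "A serious adverse event is any adverse event that results in any of the following outcomes". SAEs go to the primary investigator within 24 hours.

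Section 9 stops recruitment and analyses the safety data for "any grade 3 or greater toxicity on any subject that can be directly attributed to SBRT", with no time limit. It adds continuous safety review, a database of all adverse events, and expedited reporting of serious, related and unexpected events. On size, "we plan to enroll 18 patients over 1-2 years with a goal of 12 evaluable cases". The plan is to publish acute and late toxicity descriptively. The progress report form in Appendix C asks only for the number of withdrawals and the reasons.

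**The concern.** The pause covers every subject, but 4.3.3 removes some irradiated subjects from the protocol and hands them to routine care. If staff take withdrawal in its ordinary sense, protocol visits end, and with them the planned collection of adverse events. A bleed or perforation some months later could be attributed to SBRT by a treating physician and still not reach the study while it is recruiting.

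These patients also carry particular information. They keep the irradiated duodenum, which pancreaticoduodenectomy removes. Late duodenal injury, one item in the 6.3 list, is essentially unobservable after the planned operation, although gastric, remaining-bowel and anastomotic events are not. Without data from unresected patients, the published late toxicity would say almost nothing about the duodenum.

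A smaller part of the gap is early. Section 6.1 calls events acute when they occur 1 to 4 weeks after SBRT and before resection. A patient whose laparotomy is aborted at week 2 would leave the protocol with up to two weeks of that window still to run.

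**Working it through.** The plan gives no attrition figure or formula behind 18 and 12, so there is nothing of its own to reproduce. The question is how often the rule would be used, and how often that would lead to a missed pause.

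**Inputs from the protocol**
- 18 enrolled for 12 evaluable, accrual over T = 12 to 24 months (Section 9). At most 18 − 12 = 6 non-evaluable patients are allowed for, with no breakdown by reason.
- The proton study in Section 1: 11 of 15 resected, so 4 of 15 (27%, exact 95% CI 8% to 55%) not resected, none because of toxicity. The reasons are not given.
- The locally advanced SBRT series in Section 1: 5% late grade 3+ toxicity, after induction chemotherapy, with 7-10 Gy per fraction at the vessels and 5-6 Gy elsewhere. This protocol gives 5 Gy per fraction without chemotherapy, so the 5% is only a guide.

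**Assumptions (not in the protocol)**
- s, the share of unresected patients who fail for advanced disease: a quarter, half or all.
- p, the rate of late grade 3+ events attributed to SBRT: 2% or 5%.
- u, the share of such events the study does not learn of: one half.
- Event lag L spread evenly over months 1 to 12, even accrual, deaths ignored.

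**Step 1: expected use of the rule.** Expected unresected = 18 × 4/15 = 4.8. Expected withdrawn n = s × 4.8 = 1.2 (quarter), 2.4 (half) or 4.8 (all). Chance that the rule is used at least once = 1 − (1 − s × 4/15)^18 = 71%, 92% or over 99%.

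**Step 2: share of events falling while recruitment is open.** The mean lag is 6.5 months, so w = 1 − 6.5/T = 0.458 for T = 12 and 0.729 for T = 24.

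**Step 3: chance of a missed pause** = 1 − (1 − p·w·u)^n.

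| Withdrawn (n) | p = 5%, T = 12 | p = 5%, T = 24 | p = 2%, T = 12 | p = 2%, T = 24 |
|---|---|---|---|---|
| 1.2 (quarter) | 1.4% | 2.2% | 0.55% | 0.9% |
| 2.4 (half) | 2.7% | 4.3% | 1.1% | 1.7% |
| 4.8 (all) | 5.4% | 8.5% | 2.2% | 3.5% |

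For example, with half failing and T = 12: 1 − (1 − 0.05 × 0.458 × 0.5)^2.4 = 2.7%. With nobody withdrawn the chance is 0.

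**Step 4: what fuller follow-up could show.** With 0 events in 4 patients the exact 95% upper limit is 60%; with 0 in 6 it is 46%. The gain is detection of individual events, not an estimate of a late rate.

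**The case against.** The strongest reply is that the text already covers these patients. Section 6.1 speaks of the course of the study, not of the patient's participation, and the study is by definition running while recruitment is open. On that reading a perforation in a withdrawn patient is an adverse event, is an SAE if it has a listed outcome, and counts under the words covering any subject. Section 4.2(d) is met by a visit to any of three oncology services, so routine care may satisfy it. The clock in 6.3 runs from treatment. Section 9's database is of all adverse events. Section 8 puts trial enrolment in the electronic medical record, where treating physicians at this single centre can see it. Section 4.3.3 sits under treatment, so withdrawal could mean only that protocol treatment ends. The more detailed action paragraphs in Section 9 also concern whether a patient reaches surgery, which suggests that the pause was not designed with late events in mind.

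Much of this stands. It is a reasonable reading and it lowers the likely loss. It does not remove the conflict, because 4.3.3 explicitly withdraws the patient from the protocol and none of the general rules says that it survives this. A safety trigger should not depend on which reading staff adopt.

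A reader might infer more than the documents support:
- *That withdrawn patients are excluded from the pause.* They are not; the trigger applies to any subject. What is missing is assurance that the data reach it.
- *That the long-term evaluation leaves out unresected patients.* The Section 9 sentence about all 12 patients sets when that evaluation takes place; it does not exclude anyone.
- *That a listed objective fails.* Late toxicity is not listed in 2.2 or 2.3, and the acute objective is touched only through the short window described above.
- *That about six further patients would be put at risk.* Under the lag assumption, 5.5 (T = 12) to 6.8 (T = 24) patients would on average remain to be enrolled after such an event. That is conditional on the event occurring during recruitment, and Section 9 lets recruitment resume after review, so they might be enrolled anyway.

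**Conclusion.** The point holds as a gap in assurance: no text says that adverse event collection continues after withdrawal under 4.3.3, although several provisions can be read that way. The rule is likely to be used at least once, but the chance that it causes a missed pause is small. It is about 1% to 4% with a quarter to half of unresected patients failing for advanced disease, a 5% event rate and half of events not learned of. At a 2% event rate it is about 0.5% to 2%. The figures of 5.4% to 8.5% at a 5% rate need every unresected patient to have failed for advanced disease, which the protocol does not show. The event rate, the lag and the share not learned of are all assumptions, and ignoring deaths pushes the figures up. No estimate or sample size changes. The case for acting is that this is a safety trial, the ambiguity touches its recruitment pause, and one sentence removes it.

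**What to change.** In 4.3.3, replace the withdrawal with wording such as: protocol treatment ends; the patient stays in adverse event and SAE follow-up under 4.2 and 6.2 to 6.4, by visit, telephone or chart review, unless consent is withdrawn; and SBRT-attributed grade 3+ events count toward the Section 9 rule. Apply this to every irradiated patient who is not resected, whatever the reason. Report their late events case by case, not as a rate.

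The cost is a short amendment, consent wording if needed, and light data collection in at most about 6 patients, mostly from routine visits or the chart. Some will be treated elsewhere or die early, and tumour progression, stents and chemotherapy will make attribution to SBRT harder. Dose, surgery and sample size are unchanged.

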#### 4.3.4 Adjuvant Therapy

Adjuvant chemotherapy may be given after pancreaticoduodenectomy at the discretion of the medical oncologist.

Postoperative radiotherapy would not routinely be given after SBRT.

#### **4.4 Cost of Treatments to the Subject**

Some of the tests/procedures/exams involved in the study such as imaging and laboratory analysis for oncologic staging and the surgical resection are standard care. The patient and/or his/her insurance company will be responsible for paying for any tests/procedures/exams that are done as part of the standard of care. The patient and his/her insurance company will also be required to pay for the SBRT radiation received through this study. The provider will attempt to obtain prior authorization for the radiation treatment from the subject's insurance provider. Any difficulties obtaining authorization will be discussed with the subject prior to your treatment.

The patient will be encouraged to discuss their coverage with the insurance provider prior to initiating treatment. The cost of SBRT will be offset by omitting fractionated radiotherapy that would otherwise be given as the standard of care after surgery and chemotherapy.

There will be no payments made to patients on the study.

## **5        EVALUATION OF EFFICACY**

### **5.1      After Radiation**

No routine oncologic evaluation will be performed after SBRT therapy. Further workup may be needed if patients demonstrate clinical signs of disease progression.

### **5.2      After Surgery**

#### **5.2.1    Pathology**

Following surgical resection, all patients will undergo pathologic staging according to the AJCC Cancer Staging Manual, 7th Edition including T,N,M staging. Pancreatic transection margin, bile duct, and uncinate margin will be evaluated on frozen section. Recorded on permanent section will be: tumor size, degree of differentiation (well, moderate, poor), lymph node status, margin status. The amount of necrosis in the tumor and any other effects of treatment should also be noted.

